9.2 SAMPLE SIZE DETERMINATION

Planned Sample Size and Feasibility

The total number of participants planned for enrollment is 50, which includes a buffer to account for expected attrition.

Outcome Measure Used for Sample Size Calculations

Return to unrestricted dance participation at 12 months, a binary (yes/no) outcome.

Test Statistic

A Fisher's exact test will be used to compare the proportion of participants who return to unrestricted dance between experimental and control groups (dichotomized by a median split or similar method).

Statistical Hypotheses

Null Hypothesis (H_0): There will be no difference in self compassion scores to return to unrestricted dance at 3 months between the mental health app group and control group.

Alternative Hypothesis (H_1): Self compassion and return to unrestricted dance is expected to be improved in the mental health app treatment group compared to control group.

Assumptions for Sample Size Calculation

- Alpha (Type I error rate): 0.05 (two-tailed)
- Power (1 - Beta): 0.80 (80%)
- Effect Size: Odds Ratio (OR) = 5.0
- Expected Proportions:
 - Control group: 60% expected to return to dance
 - Experimental: 95% expected to return to dance
- These assumptions are informed by preliminary data and theoretical rationale suggesting that higher self-compassion is strongly associated with better emotional regulation, adherence to rehabilitation, and psychological resilience—all of which plausibly contribute to better recovery outcomes in dancers (Zarzycki et al., Gennarelli et al., Christino et al.).

Statistical Method and Software

- Sample size was calculated using:
 - Validated using G*Power 3.1 (Faul et al. 2007)
- Using these assumptions, the required sample size is:
 - 38 participants total (19 per group) to detect an OR of 5.0 with 80% power at $\alpha = 0.05$.
- Missing data on the primary endpoint (i.e., return to dance status at 12 months) will be minimized through close follow-up and contact strategies. If missing data occur, analyses will proceed using available-case analysis and sensitivity analyses will be conducted as described in Sections 9.4.2 and 9.4.3.
- Interim Analyses
 - No formal interim analyses are planned due to the small sample size and short duration of primary outcome measurement. Therefore, no statistical correction (e.g., O'Brien-Fleming or Pocock boundaries) is required.
- Sensitivity and Robustness Checks
 - Given the small sample size and reliance on a relatively large assumed effect size (OR = 5.0), the robustness of the sample size was tested under varying assumptions:

Control Group Return Rate (p_1)	Experimental Group Return Rate (p_2)	Effect Size (OR)	Required n per group	Total Sample Size
-------------------------------------	--	------------------	----------------------	-------------------

60%	95%	12.7	19	38
60%	90%	6.0	26	52
60%	85%	4.25	33	66

- This supports the feasibility of the current design to detect large effects, while highlighting that smaller effects will not be statistically detectable in this study.
-

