9.4.2 ANALYSIS OF THE PRIMARY EFFICACY ENDPOINT(S)

- The primary outcome of interest is return to dance (binary).
- The proportion of subjects in each group that returned to dance will be evaluated with Pearson's chi-square or Fisher's exact test depending on the distribution of outcomes. If there is fewer than 10 subjects in any group (control that returned to dance, control that did not return to dance, experimental group that returned to dance, experimental group that did not return to dance), Fisher's exact test will be used.
- Odds ratios will be calculated and presented for significant findings.
- Subjects will be excluded if they are missing data related to our primary outcome of interest.

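### Nineteen per group does not give 80% power for Fisher's exact test, and the stated odds ratio of 5.0 is not the 60% versus 95% contrast

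*Protocol*

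**What the plan says.** Section 9.2 bases the sample size on return to unrestricted dance at 12 months, a yes/no outcome. The test is fixed there: "A Fisher's exact test will be used to compare the proportion of participants who return to unrestricted dance". The listed assumptions are a two-sided alpha of 0.05, 80% power, "Effect Size: Odds Ratio (OR) = 5.0", and return rates of 60% (control) and 95% (experimental). The result is "38 participants total (19 per group) to detect an OR of 5.0 with 80% power".

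On enrolment the section says: "The total number of participants planned for enrollment is 50, which includes a buffer to account for expected attrition". It gives no attrition rate.

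A table follows, introduced by saying that "the robustness of the sample size was tested under varying assumptions". Its rows are:
- 60% versus 95%: odds ratio 12.7, 19 per group
- 60% versus 90%: odds ratio 6.0, 26 per group
- 60% versus 85%: odds ratio 4.25, 33 per group

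Section 9.4.2 chooses between Pearson's chi-square and Fisher's test by cell count. Fisher applies "If there is fewer than 10 subjects in any group", where the groups meant are the four cells of the arm-by-outcome table.

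**The concern.** Two inputs that should describe the same effect do not agree. The text pairs an odds ratio of 5.0 with 60% versus 95%, while the first table row gives that same contrast, at the same 19 per group, an odds ratio of 12.7. Only one can be the effect that 38 participants are meant to detect.

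Fisher's test is also conservative in small samples, and 19 per group looks like the output of a large-sample approximation. If so, the stated power belongs to a test the trial will not use.

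The power statement is what a reader will use to interpret a null result. Taken at face value, it says that an odds ratio of 5.0 would have been found four times in five. The table serves as the robustness check on the design, so errors in it hide how little the trial can detect.

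**Working it through.** **Inputs (Section 9.2):** two-sided alpha 0.05; power 0.80; control rate p1 = 0.60; experimental rate p2 = 0.95; stated odds ratio 5.0; equal groups; Fisher's exact test.

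**1. Where 19 comes from.** The unpooled normal approximation is n = (1.96 + 0.8416)² × [p1(1−p1) + p2(1−p2)] / (p2−p1)².
For 60% versus 95%: 7.849 × (0.24 + 0.0475) / 0.1225 = 18.4, so 19 per group.
The arcsine approximation gives 18.6, also 19. The exact power of the uncorrected chi-square at 19 per group is 79.6%. So 19 can be reproduced for 60% versus 95%, but not with Fisher's test. Other two-sided formulas give 22 (pooled), 27 (continuity-corrected) and 31 (Wald test on the log odds ratio).

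**2. Which test applies.** With 19 per arm, the two cells in each arm sum to 19, so at least one is below 10 and Section 9.4.2 always selects Fisher. With 25 per arm and the planning rates, the chance that all four cells reach 10 is about 1 in 10 million.

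**3. Odds ratios.** OR = [p2/(1−p2)] / [p1/(1−p1)], with control odds 0.60/0.40 = 1.5.
- 95%: 19/1.5 = 12.67
- 90%: 9/1.5 = 6.00
- 85%: 5.667/1.5 = 3.78 (the table says 4.25)
- OR 5.0: experimental odds 5 × 1.5 = 7.5, so p2 = 7.5/8.5 = 88.2%

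**4. Exact Fisher power.** Sum the product of the two binomial probabilities over all outcome pairs where the two-sided Fisher p-value is at most 0.05.

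| Contrast | OR | Protocol n per group | Fisher power at that n | Fisher n per group for 80% | Unpooled approximation |
|---|---|---|---|---|---|
| 60% v 95% | 12.67 | 19 | 68.3% | 24 | 19 |
| 60% v 90% | 6.00 | 26 | 61.6% | 36 | 29 |
| 60% v 85% | 3.78 | 33 | 52.5% | 56 | 47 |
| 60% v 88.2% | 5.00 | 19 | 39.4% | 42 | 34 |

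Rows 2 and 3 of the protocol's table are too small even under the approximation that gives 19 in row 1. Across the two-sided methods tried, row 2 needs 29 to 38 per group, row 3 needs 47 to 57, and an odds ratio of 5.0 needs 34 to 44. A one-sided pooled formula comes near row 2 (25) but not row 3 (39). No single method tried reproduces the whole table.

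**5. Planned enrolment.** Fisher power for 60% versus 95% by evaluable number per group: 22, 77.3%; 23, 79.8%; 24, 82.1%; 25, 82.2%. The requirement is 2 × 24 = 48, so the margin is 50 − 48 = 2 (2/50 = 4%). Against 38 it would appear to be 50 − 38 = 12 (24%). For an odds ratio of 5.0, power at 25 per group is 51.2%.

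**The case against.** The arithmetic is hard to dispute, so the other side rests on scope.

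- **Enrolment is 50, not 38.** At 60% versus 95%, 50 evaluable participants give 82% power, and 23 per group is almost at 80%. This stands. The enrolment target is defensible for that contrast, but only with almost no loss, and the protocol itself expects attrition.
- **The buffer of 12 is an inference.** The protocol states no attrition rate or buffer size. That is correct: 12 is only what 50 against 38 implies.
- **Withdrawn participants are to be replaced (Section 7.2).** Replacement could restore numbers. The rule is loosely worded, however, and Section 9.4.2 drops participants who lack the primary outcome, so it cannot be relied on to preserve power.
- **The limitation is disclosed.** Section 9.2 admits that it relies on a large effect and that smaller ones will be missed. Its table lists 52 for an odds ratio of 6.0, so a careful reader can see that 38 does not cover 5.0. That shows the document contradicting itself and does not repair the claim. The disclosed requirements are also too low.
- **Section 9.1 mentions logistic regression as an alternative.** Section 9.2 nevertheless fixes Fisher for the sample size, and Section 9.4.2 leads to Fisher as well.

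The odds ratios in table rows 1 and 2 are correct.

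**Conclusion.** The concern holds. With Fisher's test at a two-sided 0.05 level and equal groups, 38 evaluable participants give 68% power for 60% versus 95% and 39% for an odds ratio of 5.0; the claimed figure is 80%. With all 50 evaluable, the figures are 82% and 51%. All three sample sizes in the sensitivity table fall short for Fisher's test, and the last odds ratio is wrong. The odds ratio of 5.0 cannot be reconciled with 60% versus 95% under any test, because that conflict is in the inputs. The results rest only on the protocol's planning rates, alpha and named test. The attrition margin of 2 also assumes that lost participants are not successfully replaced.

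**What to change.** Restate Section 9.2 and keep enrolment at 50:
- Remove the odds ratio of 5.0 wherever it appears and give the effect as 60% versus 95% (odds ratio 12.7), the contrast that the protocol's own table ties to 38.
- Replace the claim of 80% power at 38 with the exact Fisher figures: 68% with 38 evaluable, 82% with 50 evaluable, and 48 evaluable needed for 80%.
- State an expected attrition rate and the power that remains after it.
- Correct the table to 24, 36 and 56 per group (48, 72 and 112 in total), with an odds ratio of 3.78 in the last row.

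This costs wording and a table, and the stated figures become less favourable. No participants are added. That depends on 60% versus 95% being the intended target: if the sponsor meant an odds ratio of 5.0, 84 evaluable participants are needed and 50 is not enough.

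Optionally, Boschloo's unconditional exact test could be named as the primary test. It holds type I error at or below 5% and raises power for 60% versus 95% to 78% at 19 per group and 87% at 25 per group, with no added participants. Sections 9.1 and 9.4.2 would then need to change to match.

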9.3 POPULATIONS FOR ANALYSES

- Intent-to-Treat (ITT): All participants who initiate treatment
- Per-Protocol (PP): Participants with full follow-up data and $\geq 80\%$ adherence to recovery protocol
- Safety Population: All participants (reporting adverse events and reinjury)
- Exploratory Subgroups: Participants may be stratified into tertiles or above/below median self-compassion for exploratory comparisons

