5.2 EXCLUSION CRITERIA

An individual who meets any of the following criteria will be excluded from participation in this study:

1. Dance is not a primary sport or less than 3 days per week spent dancing prior to injury (skater, gymnast, other sport)
2. Requiring surgery or prior surgery for the injury being treated
3. Injury outside of the leg below the knee
4. Known eating disorder or bone density issue (documented abnormal Z score and/or eating disorder diagnosis upon review of the medical chart)
5. Verbalized plans to not return to dance after recovery from the injury

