6.4 STUDY INTERVENTION COMPLIANCE

Email reminders will be sent through the app by the study team to remind the subject to complete their exercise(s). Subjects in the study group will be asked if they have been participating in the app usage and/or PT exercises prescribed at their clinic visits. The study staff will serve as a "host," and new treatment arm participants will be added to a group that is managed by the "host"/study staff. The host account has the capability to see whether a participant has completed daily exercise(s) or not. Noncompliance will be determined as a subject not registering in the app, or not using the app at all. If a subject is using the app less than prescribed, they will still be included but we will make note of their number of activities completed and will verbally inquire about their app usage at their following clinic visit.

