7.2 PARTICIPANT DISCONTINUATION/WITHDRAWAL FROM THE STUDY

Participants are free to withdraw from participation in the study at any time upon request.

An investigator may discontinue or withdraw a participant from the study for the following reasons:

- Failure to follow up
- Change of mind regarding randomization
- Significant study intervention non-compliance, defined as not registering in or using the app once
- If any clinical adverse event (AE), laboratory abnormality, or other medical condition or situation occurs such that continued participation in the study would not be in the best interest of the participant
- Disease progression which requires discontinuation of the study intervention
- If the participant meets an exclusion criterion (either newly developed or not previously recognized) that precludes further study participation

The reason for participant discontinuation or withdrawal from the study will be recorded on the enrollment log. Research participants who sign the informed consent form and are randomized or are not randomized will be replaced.

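### The ITT set is not all randomised participants: never-users of the app and allocation-refusers can be withdrawn and replaced, and the promised missing-outcome sensitivity analyses are absent

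*Protocol*

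**What the plan says.** - **Analysis set (9.3):** "Intent-to-Treat (ITT): All participants who initiate treatment". Initiating treatment is not defined. Both arms receive physical therapy; only one receives the app.
- **Withdrawal from the study (7.2):** the investigator may withdraw a participant for "Significant study intervention non-compliance, defined as not registering in or using the app once", for "Change of mind regarding randomization", or "If the participant meets an exclusion criterion (either newly developed or not previously recognized) that precludes further study participation". One exclusion criterion in 5.2 is "Verbalized plans to not return to dance after recovery from the injury".
- **Replacement (7.2):** "Research participants who sign the informed consent form and are randomized or are not randomized will be replaced".
- **Compliance (6.4):** "Noncompliance will be determined as a subject not registering in the app, or not using the app at all". For partial use, however, "If a subject is using the app less than prescribed, they will still be included".
- **Stopping the app (7.1):** a participant who discontinues the exercises stays in the study and completes the remaining procedures.
- **Missing outcomes:** 9.2 plans an available-case analysis and refers to 9.4.2 and 9.4.3 for sensitivity analyses. Both of those sections state only that participants with missing data are excluded.
- **Blinding (6.3):** none.

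**The concern.** An intention-to-treat comparison is valid because the groups are those that randomisation formed. Here the set can be changed after allocation is known, and one of the routes exists in one arm only: a control participant cannot fail to register in an app that controls do not receive. If people who never open the app are also less likely to return to dance, removing them raises the app arm's return rate and leaves the control arm's unchanged. Section 9.2 itself links psychological resilience and adherence to better recovery, so such an association is plausible.

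The newly developed exclusion criterion adds a route in either arm. A participant who says after randomisation that they will not return to dance has nearly declared the primary outcome, yet could be withdrawn for it.

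With about 25 participants per arm, a few removals can decide the result. A reader who sees the label ITT would have no reason to suspect them.

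**Working it through.** **1. Who is lost at each step**

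| Rule | Who can be lost | Arm |
|---|---|---|
| 9.3, treatment read as physical therapy | those who never start it | either |
| 9.3, treatment read as the app | those who never start it | app only |
| 7.2, never registered or used | never-users | app only |
| 7.2, change of mind about randomisation | refusers | either |
| 7.2, new exclusion criterion | includes those who now plan not to return | either |
| 9.4.2, missing outcome | anyone without return status | either |

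Sections 6.4 and 7.1 protect partial users and those who stop the app. Neither clearly brings back never-users or refusers.

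**2. Effect of removing never-users**

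From 9.2: control return 60%, two-sided alpha 0.05, Fisher's exact test, 50 enrolled (25 per arm if allocation is equal). Assumed, not in the protocol: no true effect, so both arms return at 60%; a share *f* of the app arm never uses the app and returns at rate *r*; never-users are removed and replaced, so 25 per arm are analysed.

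Rate among those kept in the app arm = (0.60 − *f·r*)/(1 − *f*). For *f* = 0.20 and *r* = 0.40: (0.60 − 0.08)/0.80 = 0.65. The odds ratio is against 60% (odds 1.5). Rejection rates come from full enumeration of the two binomials.

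| *f* | *r* | App rate kept | OR | Type I error | False wins for app |
|---|---|---|---|---|---|
| 0 | – | 60.0% | 1.00 | 3.0% | 1.5% |
| 10% | 40% | 62.2% | 1.10 | 3.1% | 2.1% |
| 10% | 20% | 64.4% | 1.21 | 3.6% | 3.0% |
| 20% | 40% | 65.0% | 1.24 | 3.8% | 3.3% |
| 20% | 20% | 70.0% | 1.56 | 7.0% | 6.8% |
| 30% | 40% | 68.6% | 1.45 | 5.8% | 5.6% |
| 30% | 20% | 77.1% | 2.25 | 16.8% | 16.8% |
| 20% | 60% | 60.0% | 1.00 | 3.0% | 1.5% |
| 20% | 80% | 55.0% | 0.81 | 4.2% | 0.6% |

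The nominal one-sided share is 2.5%. Without replacement (20 v 25), the case *f* = 20%, *r* = 40% gives a type I error of 4.2%.

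**3. Effect of dropping missing outcomes**

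Same null, with outcomes lost only among non-returners. If 30% of app-arm non-returners and no controls are lost, the observed app rate is 0.60/(1 − 0.40 × 0.30) = 68.2% and type I error is 6.4%. At 50% lost, the rate is 75.0% and the error 13.2%. If 30% are lost in both arms, the error is 3.2%, but both return rates are overstated at 68.2%.

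**4. Why the missing sensitivity analysis matters**

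Section 9.2 requires 38 and enrols 50, which implies attrition of 1 − 38/50 = 24%, or 19 of 25 observed per arm. Take illustrative results near the planned rates:

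- Available case, 18/19 v 11/19: Fisher p = 0.019.
- All missing counted as not returned, 18/25 v 11/25: p = 0.085.
- Least favourable to the app (its 6 missing not returned, the 6 missing controls returned), 18/25 v 17/25: p = 1.0.

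The same observed data run from significant to no difference, depending on an assumption the protocol says it will examine and does not.

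**The case against.** - **No set is tied to the primary test.** Section 9.4.2 does not name the ITT set; it compares the groups and excludes only missing outcomes, and the assignment may sit in an unseen SAP. This is fair as to certainty. But ITT is the natural default and is misdefined here, and an SAP cannot recover 12-month outcomes that were never collected.
- **The wording is permissive.** Withdrawal is something the investigator may do, and the replacement sentence, read literally, covers everyone who consents. It does not say that the replaced participants' data are discarded. This stands as a reading of the text. It makes the rule unclear rather than safe, because discretion is exercised with allocation known.
- **Never-use may be rare.** Staff help participants log in, the app sends reminders, and willingness to comply is an entry criterion. No figure in the protocol supports 20% or 30%. At 10%, type I error is 3.1% to 3.6%, and even 20% returning at 40% stays under 5%. This stands: the large inflations need high never-use with poor return, or heavy loss of non-returners in one arm.
- **The exclusion-criterion route is speculative.** It applies only where the criterion precludes further participation, and a stated intention may never be used this way after randomisation. It is a secondary point.
- **Excluding missing outcomes agrees with the available-case plan in 9.2.** True. The defect is confined to the reference to sensitivity analyses that are not there.

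**Conclusion.** The concern holds and must be fixed. The protocol's ITT definition is wrong as written, the withdrawal and replacement rules allow removal after randomisation on a ground that exists in only one arm, and the sensitivity analyses that 9.2 points to do not exist. These are statements in the protocol, not details left to an SAP.

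The bias is likely, but not certain, to favour the app. Under the assumptions above it runs from negligible (10% never-users) to a type I error of 16.8% (30% returning at 20%). It vanishes if never-users return as often as the rest and reverses if they return more often. No figure in the protocol says which case applies, and without the promised sensitivity analyses the report would not show it either.

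**What to change.** 1. In 9.3, define ITT as all randomised participants analysed in the arm assigned, and name it in 9.4.2 as the set for the primary test.
2. In 7.2, remove app non-use and change of mind about randomisation as reasons for investigator withdrawal from follow-up and analysis. Reconcile 7.2 with 6.4 and 7.1.
3. Keep collecting 12-month return status on these participants, and on those who later meet an exclusion criterion, unless consent is withdrawn. Section 7.1 already does this for those who stop the app. Align the removal rule in 5.4.
4. State that replacements add to the randomised participants and never substitute for them.
5. Write the promised sensitivity analysis into 9.4.2, for example best/worst case or tipping point. Counting missing as not returned should be one scenario, not the primary rule: if 20% of controls alone were lost regardless of outcome, their rate would fall to 0.60 × 0.80 = 48% and type I error would be 10.0%. Add the matching text to 9.4.3 or remove the reference to it.

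The cost is protocol wording, continued follow-up of a few participants and a small extra table. Including never-users may dilute the estimated effect. If the planned 95% is meant as the rate among users and never-users return at 60%, 10% never-use gives 0.9 × 95% + 0.1 × 60% = 91.5% and lowers exact power at 25 per arm from 0.82 to 0.66; 20% gives 88% and power 0.50. That loss belongs in the sample-size discussion and is no reason to exclude these participants.

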9.4 STATISTICAL ANALYSES

9.4.1 GENERAL APPROACH

- Descriptive statistics will be presented. Continuous data will be evaluated with the Shapiro-Wilk test of normality, data that is considered normal with that test will be evaluated with Levene's test of homogeneity of variances. Data that are found to be parameteric with both tests, will be treated as normally distributed and evaluated with analysis of variance (ANOVA). Continuous data that fails either test of normality listed above will be evaluated with the Mann-Whitney U. Continuous data will be presented as means \pm standard deviation, with the range. Non-parameteric continuous data will include the median as well.
- Categorical data will be evaluated with Pearson's Chi-square, or Fisher's exact test. Odds ratios will be calculated for categorical data that is found to be significantly different among the two groups.
- Statistical significance will be defined as $p < 0.05$.

